1.2.4. Study Procedures

The schedule of assessments, as outlined in the study protocol, is presented in [Table 1](#). The study flow is presented in [Table 2](#).

Table 1: Schedule of Assessments

[figure not shown]
Visit Name (Day)	Screening (Day 0)	Day 1A	Day 1B	Visit 1R	Week 1 (Day 7)	Week 2 (Day 14)	Week 3 (Day 21)	Week 4A (Day 28)	Visit 4B	Visit 4R	Week 6 (Day 42)	Unscheduled Visit
Visit Window in Days	-14 to -7	-7 to -1	-1 to 0		+/-1	+/-1	+/-1	+/-1	+/-1		+/-3	
Informed Consent	X											
Inclusion/Exclusion Criteria												
Demographics												
Medical History												
Concomitant Medications											X	X
Smoking Status	X											
Physical Exam	X											X
Body Weight	X				X	X	X	X			X	
Height	X											
12-Lead ECG	X											X
Clinical Chemistry ^{1, 2}	X							X				
Blood for Biomarkers ³			X			X		X				X
In-Clinic BP and HR	X	X			X	X	X	X			X	X
Urine Pregnancy Test for WOCBP ⁴	X											
ABPM placement ⁵		X		X				X		X		
ABPM Removal			X	X					X	X		
IWRS			X									
Dispense Investigational Product to Patient			X									
Investigational Product Application ⁶			X						X ⁷			

Visit Name (Day)	Screening (Day 0)	Day 1A	Day 1B	Visit 1R	Week 1 (Day 7)	Week 2 (Day 14)	Week 3 (Day 21)	Week 4A (Day 28)	Visit 4B	Visit 4R	Week 6 (Day 42)	Unscheduled Visit
Visit Window in Days	-14 to -7	-7 to -1	-1 to 0		+/-1	+/-1	+/-1	+/-1	+/-1		+/-3	
Investigational Product Compliance ⁸			X						X			X
Counseling ^{9, 10}		X	X									
Soap and Shampoo ¹¹			X		X	X	X	X	X ^{7, 12}			
Study Diary ¹³			X		X	X	X	X				X
Skin Swabs ¹⁴			X								X	X
AEs ¹⁵			X								X	X

Abbreviations: ABPM=Ambulatory blood pressure monitoring, AE=Adverse event, BP=Blood pressure, ECG=Electrocardiogram, IWRS=Interactive web response system, HR=Heart rate, IP=Investigational product, WOCBP=Woman of child-bearing potential.

1. Patients should fast for at least 8 hours before the test. Blood for clinical chemistry will be shipped to the central lab for processing.
2. Blood for HbA1C only will be drawn at the Week 4A visit and shipped to central lab or processing.
3. Blood samples for biomarkers will be collected and processed on site. Patients should fast for at least 8 hours before the test. Samples will then be frozen onsite and shipped on monthly bases to the Central lab for storage.
4. Urine pregnancy test for WOCBP will be done at Screening.
5. If subject undergoes ABPM procedures and equipment fails, subject will be scheduled for another ABPM session within 48 hours for Visit 1R or 4R.
6. Subjects will be asked to apply the IP twice daily as per their randomization. First IP application will happen in the office under medical supervision.
7. In the event that subject fails the ABPM test on Visit 4B and needs to repeat it, subject should continue applying the IP through Visit 4R. Investigational product and soap/shampoo should be returned to the site on Visit 4R. Every effort should be made by the site to schedule Visit 4R as close to Visit 4B as possible.
8. Weight of an IP kit will be obtained at the at the 1B visit. Weight of an individual bottle that is currently in use will be obtained at each visit. Final weight of the kit will be obtained at Week 4B visit, when kit is returned by the patient.
9. Subjects will be counseled on the use of study medication, diary and answer any questions subject may have.
10. Subjects will be counseled on the use of ABPM equipment.
11. Subjects are to be provided soap and shampoo at Baseline visit. However, soap and shampoo is available upon request in the event that subjects run out of their initial supplies.
12. Soap and shampoo should be returned to the Study Coordinator.
13. Subjects will be asked to fill out study diary for the duration of the study (Baseline-Day 28).
14. Skin swabs will be obtained during the office visit and will be frozen in the -80 freezer and will be shipped monthly to Biostorage labs.
15. AEs will be monitored throughout the trial.

Table 2: Study Flow

1.2.5. Efficacy Parameters

- Difference in mean in-clinic systolic blood pressure between the active and vehicle groups.
- Difference in mean in-clinic diastolic blood pressure between the active and vehicle groups.
- Difference in mean ambulatory systolic and diastolic blood pressure.

1.2.6. Safety Parameters

Safety and tolerability endpoints will consist of all adverse events (AEs) reporting during the study duration.

1.2.7. Exploratory Parameters

- Difference in inflammatory biomarkers between active and vehicle groups.
- Microbial content, microbiota composition, and B244 presence/absence at baseline and Day 28.

2. SUBJECT POPULATION

2.1. Population Definitions

The following subject populations will be evaluated and used for presentation and analysis of the data:

- Intent-to-Treat (ITT) Population: Includes all randomized participants. Subjects will be analyzed according to the treatment assigned by the randomization schedule. The ITT population will be the primary population for efficacy analyses.
- Safety Population: Includes all subjects who received at least 1 dose of study medication. Subjects will be analyzed according to the study drug received.
- Per Protocol (PP) Population: Subjects who have baseline and Day 28 post-baseline in-clinic systolic or diastolic blood pressure measurement, and did not have any major protocol violations which could potentially compromise interpretation of results. The PP population will be used for supportive summaries of efficacy data.
- Ambulatory Blood Pressure Monitoring Population (ABPP): Subjects in the Safety population who had valid baseline and Day 28 ambulatory blood pressure monitoring (ABPM) measurements. Subjects who repeated the ABPM are included in the population if the repeated assessment met the device monitor's criteria for "passing."

The ITT population is the primary population for the analysis of efficacy parameters. A subset of efficacy parameters will be evaluated for the PP population (see [Section 4.3](#)). The Safety population is the primary population for the analysis of safety endpoints.

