## **15.2 Populations for Analysis**

ITT: includes all randomized participants.

Safety: includes all subjects who received at least 1 dose of study medication.

Per Protocol: subjects who administered at least 50 % of IP , have at least one baseline and post baseline in clinic systolic blood pressure measurement , and did not have any major protocol violations.

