2.2. Protocol Violations

All the following deviations will be summarized on the ITT patient population and may include:

- Inclusion or exclusion criteria not satisfied.
- Deviations related to the IP administration.
- Repeated use of soap or shampoo other than the products provided by AOBiome.

At the discretion of the Sponsor, major protocol violations, as determined by a review of the data prior to unblinding of the study results and the conduct of statistical analyses, may result in the removal of a subject's data from the PP population. The Sponsor or designee will be responsible for producing the final protocol violation file (formatted as a Microsoft Excel file), in collaboration with Veristat and the data monitoring group as applicable; this file will include a description of the protocol violation and clearly identify whether or not this violation warrants exclusion from the PP population. This file will be finalized prior to hard database lock.

All protocol violations will be presented in a data listing.

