4.3.1. Weekly In-Clinic Blood Pressure

To assess treatment effect, change from baseline in weekly systolic and diastolic blood pressure values will be analyzed using a mixed effect model that includes the change from baseline at Days 7, 14, 21, and 28. Day 42 will not be used in the primary endpoint analysis. The model will include stratification factors of spray number and hypertension and baseline blood pressure as covariates, with treatment group (B244 or placebo) and visit as fixed effects, and subject as a random effect. The model will include the following interaction terms: treatment*visit, strata*visit, treatment*strata, and treatment*strata*visit. Estimates of the adjusted LS mean, difference in LS means, and corresponding 95% CIs will be obtained from the model.

Linear contrasts of the differences between each treatment group (4 doses or 8 doses) and placebo at each visit will be used to compare the results between treatments using LS means between each active treatment group and placebo. Nominal 2-sided p-values and 95% CIs will be reported at Days 7, 14, 21, and 28.

Treatment group comparisons within each strata will be an exploratory analysis.

Mixed models will be implemented using PROC Mixed in SAS, using an unstructured within-subject covariance matrix and denominator degrees of freedom from the Kenward-Roger method. Other covariance matrices (first order autoregressive process [AR(1)], compound symmetry, independent) may be utilized in the event that the unstructured matrix does not converge. In this event, the matrix structure that converges provides the lowest akaike information criterion (AIC) value will be selected.

This modeling will be performed for both systolic and diastolic blood pressure, in both the ITT and PP populations.

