5. CHANGES TO PLANNED ANALYSES

The following changes between the study protocol are described below.

Editorial edits have been made in [Section 1.1.1](#) (Introduction), [Section 1.2.1](#) (Synopsis of Study Design), [Section 1.2.2](#) (Randomization Methodology), and [Section 1.2.5](#) (Efficacy Parameters) to clarify the information from the study protocol.

The schedule of events was changed according to an administrative letter from AOBiome dated 08 February 2017. Subjects were instructed to continue use of IP through end of the ABPM monitoring period (Day 29 [Visit 4B] and to weigh the IP after this visit. Subjects who had already completed the Day 29 visit prior to the notification should have used the IP through Day 28 and weighed the product on this visit.

The SD in the sample size was changed from 11 to 10.5 in order to estimate power correctly.

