7.1.1. Statistical Table Shells

The following tables will be produced.

STATISTICAL TABLES

Table 14.1.1

Subject Enrollment and Disposition (All Enrolled Subjects)

Disposition	Statistic	B244		Placebo		Overall (N=xx)
		4 Sprays (N=xx)	8 Sprays (N=xx)	4 Sprays (N=xx)	8 Sprays (N=xx)	
Total Number of Subjects						
Screened	n (%)	xx (xx.x)	xx (xx.x)	xx (xx.x)	xx (xx.x)	xx (xx.x)
Screen Failures [1]	n (%)	xx (xx.x)	xx (xx.x)	xx (xx.x)	xx (xx.x)	xx (xx.x)
Enrolled [1]	n (%)	xx (xx.x)	xx (xx.x)	xx (xx.x)	xx (xx.x)	xx (xx.x)
Randomized [1]	n (%)	xx (xx.x)	xx (xx.x)	xx (xx.x)	xx (xx.x)	xx (xx.x)
Treated [2]	n (%)	xx (xx.x)	xx (xx.x)	xx (xx.x)	xx (xx.x)	xx (xx.x)
Completed the Study [3]	n (%)	xx (xx.x)	xx (xx.x)	xx (xx.x)	xx (xx.x)	xx (xx.x)
Discontinued	n (%)	xx (xx.x)	xx (xx.x)	xx (xx.x)	xx (xx.x)	xx (xx.x)
Study Population [4]						
Safety	n (%)	xx (xx.x)	xx (xx.x)	xx (xx.x)	xx (xx.x)	xx (xx.x)
Intent-to-Treat (ITT)	n (%)	xx (xx.x)	xx (xx.x)	xx (xx.x)	xx (xx.x)	xx (xx.x)
Per Protocol (PP)	n (%)	xx (xx.x)	xx (xx.x)	xx (xx.x)	xx (xx.x)	xx (xx.x)
Ambulatory Blood Pressure	n (%)	xx (xx.x)	xx (xx.x)	xx (xx.x)	xx (xx.x)	xx (xx.x)
Strata						
Pre-Hypertension	n (%)	xx (xx.x)	xx (xx.x)	xx (xx.x)	xx (xx.x)	xx (xx.x)
Stage 1 Hypertension	n (%)	xx (xx.x)	xx (xx.x)	xx (xx.x)	xx (xx.x)	xx (xx.x)
Reason for Early Study Discontinuation						
Death	n (%)	xx (xx.x)	xx (xx.x)	xx (xx.x)	xx (xx.x)	xx (xx.x)
Lost to follow-up	n (%)	xx (xx.x)	xx (xx.x)	xx (xx.x)	xx (xx.x)	xx (xx.x)
Withdrawal of consent by subject	n (%)	xx (xx.x)	xx (xx.x)	xx (xx.x)	xx (xx.x)	xx (xx.x)
Investigator's decision	n (%)	xx (xx.x)	xx (xx.x)	xx (xx.x)	xx (xx.x)	xx (xx.x)
Screen Failure	n (%)	xx (xx.x)	xx (xx.x)	xx (xx.x)	xx (xx.x)	xx (xx.x)
Other	n (%)	xx (xx.x)	xx (xx.x)	xx (xx.x)	xx (xx.x)	xx (xx.x)

[1] Percentage based on the number screened.

[2] Percentage based on the number enrolled.

[3] Percentage and all subsequent percentages based on the number dosed.

[4] Safety Population: All subjects who received at least 1 dose of study medication, analyzed according to drug received.

Intent-to-Treat (ITT) Population: all randomized subjects, analyzed according to treatment assigned.

Per Protocol (PP) Population: Subjects who were administered at least 50% of , have baseline and at least 1 post-baseline in-clinic systolic or diastolic blood pressure measurement, and did not have any major protocol violations which could potentially compromise interpretation of results.

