7.1.3. Data Listing Shells

The following listings will be produced.

SUBJECT DATA LISTINGS

AOBiome LLC
Protocol AVB244-003

Confidential

Page 1 of x

Listing 16.2.1

Study Completion Status (Enrolled Subjects)

Treatment:

Strata:

Subject in Population						Date of Study	Reason for Early Discontinuation	Protocol Version
Subject Number	ITT	Safety	PP	ABPP	Date of Randomization	Date of Drug Dispense	Last Dose (Rel Day)	Withdrawal (Rel Day)
							Death	
							Lost to Follow-up	
							Withdrawal of Consent by Subject	
							Investigator's Decision	
							Screen Failure	
							Other, specify	

Intent-to-Treat (ITT) Population: All randomized subjects, analyzed according to treatment assigned.

Safety Population: All subjects who received at least 1 dose of study medication, analyzed according to drug received.

Per Protocol (PP) Population: Subjects who were administered at least 50% of study medication, have baseline and at least 1 post-baseline in-clinic systolic or diastolic blood pressure measurement, and did not have any major protocol violations which could potentially compromise interpretation of results.

Ambulatory Blood Pressure Monitoring Population (ABPP): Subjects in the Safety population who had valid baseline and Day 28 ABPM measurements. Subjects who repeated the ABPM are included in the population if the repeated assessment met the Monitor's criteria for "passing."

Rel Day = Relative to first dose of study medication, Day 1.

PROGRAM NAME: XXXXXXXXXXXXXXXXXXXXXXXXXXXXXXXXXXXXXXX

DATE: HH:MM/DDMMYYYY

AOBiome LLC
Protocol AVB244-003

Confidential

Page 1 of x

Listing 16.2.2.1

Inclusion/Exclusion Criteria Not Met

Treatment:
Strata:

Subject Number	Did the Subject Meet All Eligibility Criteria?	Criterion ID Not Met	Was a Waiver Provided so the Subject can Continue on the Trial?	Date of Waiver
		Inclusion 1	Yes	DD-MMM-YYYY
		Inclusion 2	No	
		Etc.		

PROGRAM NAME: XXXXXXXXXXXXXXXXXXXXXXXXXXXXXXXXXXXXXXX

DATE: HH:MM/DDMMYYYY

AOBiome LLC
Protocol AVB244-003

Confidential

Page 1 of x

Listing 16.2.2.2

Protocol Deviations

Treatment:

Strata:

Subject Number	Date	Visit	Description
-------------------	------	-------	-------------

PROGRAM NAME: XXXXXXXXXXXXXXXXXXXXXXXXXXXXXXXXXXXXXXX

DATE: HH:MM/DDMMYYYY

AOBiome LLC
Protocol AVB244-003

Confidential

Page 1 of x

Listing 16.2.3

Subjects Excluded from Efficacy Analyses

Treatment:
Strata:

Subject Number	Reason Excluded from PP Population

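### The SAP holds two incompatible Per Protocol definitions and does not list the change from the protocol; separately, its exposure formulas subtract in the wrong order and its bottle counts disagree

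*SAP*

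**What the plan says.** **PP population.** The documents define it in three ways; all three also exclude major protocol violators.
- SAP 2.1: "Subjects who have baseline and Day 28 post-baseline in-clinic systolic or diastolic blood pressure measurement, and did not have any major protocol violations". There is no dosing requirement.
- SAP shells: footnote 4 of Table 14.1.1 (Section 7.1.1) sets a 50% dosing floor and says patients must "have baseline and at least 1 post-baseline in-clinic systolic or diastolic blood pressure measurement, and did not have any major protocol violations". The footnote to Listing 16.2.1 (Section 7.1.3) agrees: "Subjects who were administered at least 50% of study medication, have baseline and at least 1 post-baseline in-clinic systolic or diastolic blood pressure". A word seems to be missing after the 50% in the table footnote. This may be lost in text extraction and is not counted here.
- Protocol 15.2: "subjects who administered at least 50 % of IP , have at least one baseline and post baseline in clinic systolic blood pressure measurement".

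SAP Section 5 opens with "The following changes between the study protocol are described below". It then lists editorial edits to four subsections of Section 1, a schedule letter, and the SD change from 11 to 10.5. It does not mention PP.

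PP is a supportive population. SAP 4.3.1 states: "This modeling will be performed for both systolic and diastolic blood pressure, in both the ITT and PP populations". SAP 4.3.1.1 adds the Day 28 ANCOVA in the same two populations. SAP 2.2 lets the Sponsor remove patients from PP for "major protocol violations, as determined by a review of the data prior to unblinding of the study results".

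**Exposure.** SAP 4.4.1 defines net weight as the Day 29 (or Day 28) weight less the Day 1 weight. Footnote 1 of Table 14.1.4.1A and footnote 1 of Listing 16.2.5.2 also subtract first dispense from last visit. Expected use is 7.91 g/week (4 sprays per application) or 15.82 g/week (8 sprays per application), over 28 days. Protocol 9.7 and 9.15 describe a kit of three bottles.

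**The concern.** Two current passages of one SAP version give different PP membership rules. One ties membership to a Day 28 reading and ignores dosing. The other ties it to dosing and accepts any post-baseline reading. A programmer working from the shells and one working from Section 2.1 would build different populations for the supportive systolic and diastolic models. The Day 28 rule also sits oddly with SAP 3.10, which favours the mixed model because it uses partly observed sequences. Under Section 2.1 the PP mixed model loses the sequences of patients who leave before Day 28.

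The 50% rule, where it appears, has no stated measure. Protocol 9.6 records missed doses and 9.16 weighs the product, but neither is tied to the rule. No passage says whether the 50% is of the planned course or of the time on treatment.

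In the exposure section, the stated subtraction gives negative use, and the three statements of how many bottles are weighed do not agree.

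**Working it through.** **1. Do the two SAP definitions select the same patients?** Take two patients with baseline readings and no violation rated as major.

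| Patient | SAP 2.1 | SAP shells | Protocol 15.2 |
|---|---|---|---|
| 60% of planned doses, last BP at Day 21 | out | in | in |
| 40% of planned doses, BP at Day 28 | in | out | out |

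The first case does not depend on how the 50% is read: 60% of a 28-day course taken over 21 days is 0.60 x 28/21 = 80% of time on treatment. Neither SAP set contains the other. The shells differ from the protocol only in accepting a diastolic value in place of a systolic one. That should matter little, since both come from the same reading.

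**2. How large could the difference be?** Inputs: 116 patients and 104 completers (SAP 1.2.1), and four modelled visits at Days 7, 14, 21 and 28 (SAP 4.3.1).
- Planned dropouts: 116 - 104 = 12.
- If all 12 leave after Day 21, observed values are 104 x 4 + 12 x 3 = 416 + 36 = 452.
- With full dosing to that point, these patients have 21/28 = 75% of the course and 21/21 = 100% of time on treatment. The shells keep them under either reading.
- SAP 2.1 removes their values: 36/452 = 8.0%.
- After Day 14: 14/28 = 50% of the course with no missed dose, exactly at the threshold.
- After Day 7: 7/28 = 25% of the course but 7/7 = 100% of time on treatment. The definitions differ for these patients only on the second reading.

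The Day 28 ANCOVA already needs a Day 28 value, so only the absence of the 50% rule can change its PP set.

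**3. Sign of the exposure formula.** Expected 28-day use is 4 x 7.91 = 31.64 g, or 4 x 15.82 = 63.28 g. For a fully compliant patient, last minus first is -31.64 g or -63.28 g, so percent compliance is -31.64/31.64 = -63.28/63.28 = -100%. First minus last gives +100%. The denominator in the displayed formula of SAP 4.4.1 may be broken by text extraction and is not counted.

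**4. Bottle counts (first weight / last weight).** SAP 4.4.1: 4 / 4. Table 14.1.4.1A: 4 / 3. Listing 16.2.5.2: 3 / 3. Kit in the protocol: 3.

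**5. Two smaller mismatches.**
- SAP 4.4.1 limits percent compliance to product returned at Day 28 or 29. SAP Table 1 footnote 7 has patients who repeat ABPM return it at Visit 4R. Read literally, they get no value. Their number is not given.
- SAP 4.4.1 describes a compliant patient as spraying 4 or 8 times a day. Protocol 9.7 has 4 or 8 pumps applied twice daily: 2 x 4 = 8 or 2 x 8 = 16 per day.

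**The case against.** The best defence is that Section 2.1 is the place where populations are defined, and the shells carry visibly stale text: the Table 14.2.1A footnote names an outcome, NIS-W, that is not a measure in this trial. The 50% footnotes may simply be leftovers. That is plausible. But it would make Section 2.1 a deliberate departure from the protocol on both dosing and timing, and Section 5 is silent on it.

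A second defence is that the blinded SAP 2.2 review can remove low users, since it covers deviations in product administration. It can, case by case. It sets no 50% threshold, and it cannot choose between a Day 28 reading and any post-baseline reading.

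On exposure, the intent is clear. The opening sentence of 4.4.1 names the dispensed weight first, and Listing 16.2.5.2 has a column for product used. The schedule footnotes say the whole kit is weighed at Visit 1B and at return, so a stray bottle count need not change a kit-weight difference. This stands: the exposure items are errata.

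Four stronger readings are tempting, and the documents do not support them.
- A reader might infer from "Subjects were instructed to continue use of IP through end of the ABPM monitoring period" that the 28-day expected weight is a full day short. Day 1 is the day of first dose (SAP 3.2), given at the morning visit. The Day 28 ABPM starts in the morning and runs 24 hours, so the kit comes back on the morning of Day 29. Assuming two applications on Day 1, Day 1 morning to Day 28 night is 28 x 2 = 56 applications. One more on Day 29 makes 57, and 57/56 = 101.8%. The 28-day figure fits. Replacing it with an expected weight for each patient's own period of use would be a preference, not a correction.
- A reader might count every value from early leavers as lost through Section 2.1. A Day 7 leaver is also excluded by a 50% rule based on the planned course, so those values are not a difference between the definitions.
- A reader might infer that the sign error empties PP, because no user of the product could reach +50%. No passage ties the 50% rule to the percent compliance formula.
- A reader might infer that the main result is at risk. ITT is the primary efficacy population.

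**Conclusion.** The inconsistency is real and in current text: the PP set is not determined by the SAP, the change from the protocol is not disclosed, and the exposure formulas are wrong as written. The weight is minor. Only the supportive PP analyses and the descriptive exposure tables are affected; the primary estimate and power are not.

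The 8.0% is an illustration, not a bound. It assumes that all 12 planned dropouts are randomized, leave after Day 21, took enough product, have all earlier readings, and have no major violation. Completion runs to Day 42 (Protocol 13.3), so some may leave after Day 28. SAP 1.2.1 calls the 116 consented, while SAP 3.1 calls them randomized. The -100% follows directly from the stated subtraction and the SAP's own weekly rates.

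**What to change.** Before hard database lock and unblinding:
1. Put one PP definition in SAP 2.1 and all shells: either the protocol's, or a changed one that is listed and justified in Section 5.
2. If the 50% rule is kept, state its data source (product weights, or diary and missed-dose records) and whether it is of the planned course or of time on treatment. Settle early leavers without a usable kit weight in the blinded SAP 2.2 review.
3. Define use as dispensed kit weight minus returned kit weight, keep the SAP's 28-day expected weight, and use one bottle count matching the three-bottle kit in 4.4.1, Table 14.1.4.1A and Listing 16.2.5.2.
4. Let returns at Visit 4R count for percent compliance, and reconcile the sprays-per-day wording in 4.4.1 with the protocol's twice-daily text.

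The cost is SAP text and shell edits. No new data are needed, and the blinded review is already planned.
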